## 5.6 Ulocuplumab Dose for Phase II Part of Study

The MTD or maximum dose from Phase I portion of the study will be used in the phase II part of the study. After the first six participants are accrued to the Phase II cohort, enrollment will be held to conduct a DSMC safety analysis of the first two cycles of treatment. The DSMC will determine if there have been excessive dose reductions or delays which require an amendment to the Phase II ulocuplumab dose level.

## 5.7 General Concomitant Medication and Supportive Care Guidelines

Participants will be instructed not to take any additional medications (including over-the-counter products) during the course of the study without prior consultation with the investigator. At each

visit, the investigator will ask the participant about any new medications he/she is or has taken after the start of the study drug.

### 5.7.1 Prophylactically Prescribed Medication

All prophylactic premedication administration is mandatory. Participants will be pre-medicated with 10mg of oral dexamethasone and 20mg of oral famotidine (or equivalent for either agent) 8-18 hours prior to each dose of ulocuplumab. The following premedications should be administered within 30-60 minutes prior to administration of ulocuplumab:

- IV or oral diphenhydramine 25-50 mg
- Acetaminophen 650 mg orally
- Corticosteroids (10 mg of IV dexamethasone or equivalent)
- Famotidine (or equivalent) 20 mg PO or IV

### 5.7.2 Permitted Treatments

Subjects may receive DVT prophylaxis (if needed) with LMWH, warfarin (coumadin), or similar. All anticoagulants, and/or aspirin should be held in case the platelet count is  $< 50,000 \text{ mm}^3$ .

### 5.7.3 Avoidance of Medications

- Subjects taking oral or parenteral corticosteroids should be tapered off this medication for 5 half-lives prior to the first dose of ulocuplumab and must remain discontinued from all oral and parenteral corticosteroids while participating in the study (unless used for treatment of infusion reactions, rash, antiemetic prophylaxis or as part of the protocol chemotherapy regimen or subjects on low-dose corticosteroids ( $\leq 20 \text{ mg}$  prednisone or equivalent) for chronic conditions. Investigators should discuss individual cases with the medical monitor.
- Medications that are generally considered to have a risk of causing “Torsades de Pointes” (Category 1 on <http://www.qtdrugs.org/medical-pros/drug-lists/drug-lists>). Subjects must have a washout period of  $> 7$  days prior to first dose of investigational product. Caution is warranted when administering ulocuplumab to subjects taking drugs associated with prolongation of QTc listed in Category 2: Drugs with Possible Risk of Torsades de Pointes.
- Medications that Durably Inhibit Platelet Function:  
With the exception of low-dose aspirin, subjects enrolled in this study should not take concomitant medications that durably inhibit platelet function. For such medications, a wash-out period of  $\geq 7$  days is required prior to starting treatment. Medications that directly and durably inhibit platelet function include aspirin-containing combinations, clopidogrel, dipyridamole, tirofiban, dipyridamole, epoprostenol, eptifibatide, cilostazol, abciximab, ticlopidine, cilostazol should be avoided.
- Medications that Inhibit Coagulation: With the exception of heparin including low-molecular-weight heparin (LMWH) (enoxaparin, tinzaparin, etc), or Factor X inhibitors, subjects should not take drugs that directly and durably inhibit coagulation.
- Supplements such as fish oils and vitamin E preparations should be avoided.

## CYP3A- Inhibitors/Inducers

Ibrutinib is metabolized primarily by CYP3A. Avoid co-administration with strong CYP3A4 or moderate CYP3A inhibitors and consider alternative agents with less CYP3A inhibition.

- If a strong CYP3A inhibitor (eg, ketoconazole, indinavir, nelfinavir, ritonavir, saquinavir, clarithromycin, telithromycin, itraconazole, nefazadone, or cobicistat) must be used, withhold ibrutinib treatment for the duration of inhibitor use.
- If a moderate CYP3A inhibitor (eg, voriconazole, erythromycin, amprenavir, aprepitant, atazanavir, ciprofloxacin, crizotinib, darunavir/ritonavir, diltiazem, fluconazole, fosamprenavir, imatinib, verapamil, amiodarone, or dronedarone) must be used, reduce ibrutinib to 140 mg PO QD for the duration of the inhibitor use. Avoid grapefruit and Seville oranges during ibrutinib/placebo treatment, as these contain moderate inhibitors of CYP3A.
- No dose adjustment is required in combination with mild inhibitors.

Avoid concomitant use of strong CYP3A inducers (eg, carbamazepine, rifampin, phenytoin, and St. John's Wort). Consider alternative agents with less CYP3A induction.

No chronic treatment with systemic steroids (at dosages equivalent to prednisone > 20 mg/day for more than 14 days) or other immunosuppressive agents should be used. Topical or inhaled corticosteroids are allowed.

## **5.9 Duration of Follow Up**

Participants will be followed for up to 24 months after completion of protocol therapy, or until termination from study, disease progression, initiation of new anti-neoplastic therapy, or death. Participants removed from protocol therapy for unacceptable adverse event(s) will be followed until resolution of the adverse event to at least grade 1 or less, or stabilization of the adverse event. The Sponsor-Investigator has decided to terminate all follow-up as of 12/31/22.

## **5.10 Criteria for Taking a Participant Off Study**

Participants will be removed from study when any of the following criteria apply:

- Lost to follow-up
- Withdrawal of consent for data submission
- Death
- Study termination as of 12/31/22

The reason for taking a participant off study, and the date the participant was removed, must be documented in the case report form (CRF).

For Decentralized Subject Registrations, the research team updates the relevant Off Treatment/Off Study information in OnCore.

## **6. DOSING DELAYS/DOSE MODIFICATIONS**

Dose delays and modifications will be made using the following recommendations. Toxicity assessments will be done using the CTEP Version 4 of the NCI Common Terminology Criteria for Adverse Events (CTCAE) which is identified and located on the CTEP website at: [http://ctep.cancer.gov/protocolDevelopment/electronic\\_applications/ctc.htm](http://ctep.cancer.gov/protocolDevelopment/electronic_applications/ctc.htm).

In the case of toxicity, appropriate medical treatment should be used (including transfusions, cytokine growth factors, anti-emetics, anti-diarrheals, etc.) as medically indicated. All adverse events experienced by participants will be collected from the time of the first dose of study treatment, through the study and until the final study visit. Participants continuing to experience toxicity at the off study visit may be contacted for additional assessments until the toxicity has

resolved or is deemed irreversible.

For patients who are unable to tolerate the protocol-specified dosing schedule, treatment interruption(s) and dose adjustment(s) are permitted. Adverse event attribution to ibrutinib, ulocuplumab or both agents should be determined before treatment interruptions and dose adjustments are made. For non-hematologic toxicities attributable to ulocuplumab, but not to ibrutinib, ibrutinib dosing may be continued.

Dosing of ibrutinib and ulocuplumab will both be held for any of the following hematologic conditions:

- Absolute neutrophil count (ANC) <500/uL
- Platelet count <50,000/uL
- Hemoglobin <8 g/dL

Protocol therapy may be re-started as follows:

- Recovery of ANC to  $\geq 750$  uL for ulocuplumab, and  $\geq 500$ /uL for ibrutinib
- Recovery of Platelet count to  $\geq 50,000$ /uL
- Recovery of Hemoglobin to  $\geq 8$  g/dL
- Recovery of non-hematologic toxicity to grade 1 or less

Dosing of ibrutinib will be held for any of the following ibrutinib-related conditions:

- Grade 3 non-hematological toxicity
- Grade  $\geq 2$  atrial fibrillation. Consider the risks and benefits of restarting and continuing ibrutinib treatment. If clinically indicated, the use of concomitant antiarrhythmics, rate control medications, cardiac ablation, or the use of warfarin, non-warfarin or vitamin k antagonist anticoagulants agents may be considered to prevent or control ibrutinib related atrial fibrillation

If administration of ibrutinib must be interrupted because of unacceptable toxicity, ulocuplumab should also be held. Resumption of ibrutinib treatment should be handled as follows:

- 1st Occurrence: Retreat at dose level 1 (or dose level -1 if in the opinion of the principal investigator this is in subject's best interest).
- 2nd Occurrence: Retreat at Dose level -1
- 3rd Occurrence: Retreat at Dose level -2
- 4th Occurrence: Discontinue ibrutinib

If administration of ibrutinib must be interrupted because of unacceptable toxicity, drug dosing will be interrupted or modified according to rules described in Table 6-1.

Dose re-escalations of ibrutinib will not be permitted once dose reduced to next lower dose level unless done for concurrent treatment with CYP3A inhibitors (section 5.7.3). Dose reductions are permitted down to dose level -2 in Table 6-1 before a patient is taken off study. If a participant requires a dose delay of ibrutinib for > 28 days, then the participant will be taken off study.

Table 6-1. Ibrutinib Dose Modification Guidelines

Dose Level	Dose and Schedule
1	420 mg po qD
-1	280 mg po qD
-2	140 mg po qD

Participants who must permanently discontinue Ibrutinib administration will be removed from protocol therapy.

Ulocuplomab should be held if ibrutinib is held (as noted above). Dosing of ulocuplumab should also be held for any of the following ulocuplumab-related conditions:

- Grade 3 non-hematological toxicity

If administration of ulocuplumab must be interrupted because of unacceptable toxicity, unless only delayed due to ibrutinib associated toxicity, resumption of treatment should be handled as follows:

- 1st Occurrence: Retreat at current dose (or dose level -1 if in the opinion of the principal investigator this is in subject's best interest).
- 2nd Occurrence: Retreat at Dose level -1
- 3rd Occurrence: Retreat at Dose level -2
- 4th Occurrence: Retreat at Dose level -3
- 5th Occurrence: Discontinue ulocuplumab

Dose level reduction(s) or termination for ulocuplumab will follow the rules described in Table 6-2, 6-3, or 6-4.

Dose re-escalations of ulocuplumab will not be permitted once dose reduced to next lower dose level. Dose reductions are permitted per Table 6-2, 6-3, or 6-4 before a patient is taken off study. If a participant requires a dose delay of ibrutinib for > 28 days, then the participant will be taken off study.

If administration of ulocuplumab must be interrupted because of unacceptable toxicity, drug dosing will be interrupted or modified according to rules described in Table 6-2, 6-3, and/or 6-4. Treatment with ulocuplumab may be delayed and schedules adjusted if holding ulocuplumab is necessary. Ibrutinib therapy can be continued throughout ulocuplumab hold period unless the adverse event may also be related to ibrutinib. In such situations, treatment hold and/or dose modifications may be made for both drugs per Table 6-1 (for ibrutinib) and Table 6-2, 6-3, & 6-4 (for ulocuplumab).

Dose hold and de-escalation for ulocuplumab for the Phase II portion of the study will follow the rules for the cohort deemed to represent the maximum dose or MTD from the Phase I part of the study and shown in Table 6-2, 6-3, & 6-4. If a participant requires a dose delay of ulocuplumab

for > 28 days, then ulocuplumab will be discontinued. For participants permanently discontinuing ulocuplumab, ibrutinib therapy may be continued alone for study duration.

**Table 6-2. Ulocuplumab Dose Modification Guidelines Cohort 1**

Cohort dose level 1	Ulocuplumab Dose Level 1	Dose level - 1	Dose level - 2
Cycle 1	400mg	200mg	STOP
Cycle 2-6	800mg	400mg	200mg

**Table 6-3 Ulocuplumab Dose Modification Guidelines Cohort 2**

Cohort dose level 2	Ulocuplumab Dose Level 1	Dose level - 1	Dose level - 2	Dose level - 3
Cycle 1	800mg	400mg	200mg	STOP
Cycle 2-6	1200mg	800mg	400mg	STOP

**Table 6-4 Ulocuplumab Dose Modification Guidelines Cohort 3**

Cohort dose level 3	Ulocuplumab Dose Level 1	Dose level - 1	Dose level - 2	Dose level - 3	Dose Level -4
Cycle 1	800mg	400mg	200mg	STOP	-
Cycle 2-6	1600mg	1200mg	800mg	400mg	STOP

### Potential for IgM flare

Abrupt increases in serum IgM levels following administration of anti-CD20 monoclonal antibodies and intravenous immunoglobulin are well recognized in WM patients ([name] et al, 2004, Ghobrial et al, Cancer 2004). Such abrupt increases can prompt symptomatic hyperviscosity in patients with high serum IgM levels and can contribute to worsening of IgM related morbidity such as cryoglobulinemia, cold agglutinemia, and demyelinating neuropathy ([name] et al, 2015). Plasmapheresis is therefore used to treat symptomatic IgM flares, as well as prophylax in patients with high serum IgM levels (>4,000 mg/dL). Following plasmapheresis, serum IgM levels will return to steady state in 4-5 weeks. As such WM patients will be invaluable for response purposes. It is recommended patients with symptomatic hyperviscosity or a pre-treatment serum IgM level >4,000 mg/dL undergo plasmapheresis before treatment with ulocuplumab. Treatment with ulocuplumab may be delayed for up to two weeks if plasmapheresis is warranted. Close serial monitoring of serum IgM levels (at least weekly) is recommended for all participants during cycle 1, and at least every other week during cycles 2-6. For purposes of dose limiting toxicity, an IgM flare will not count given the expected nature of the flare with antibody therapy in WM patients.

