## 11. MEASUREMENT OF EFFECT

### 11.1.1 Definitions

**Evaluable for toxicity:** All participants who receive at least one dose of study treatment will be evaluable for toxicity from the time of their first treatment.

**Evaluable for objective response:** Only those participants who have measurable disease present at baseline, have received at least one cycle of therapy, and have had their disease re-evaluated will be considered evaluable for response. These participants will have their response classified according to the definitions stated below. (Note: Participants who exhibit objective disease progression or die prior to the end of cycle 1 will also be considered evaluable.)

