## 13.2 Sample Size, Accrual Rate and Study Duration

A maximum of 18 patients will be accrued for the phase I study.

A maximum of 20 evaluable patients will be accrued for the phase II study. To be evaluable for response, patients must have one cycle of therapy. Patients inevaluable for response will be replaced. Assuming an H0 of major response rate of 50% vs. an H1 of 80%, a sample of 20 patients would have a power of 80% with an alpha of 0.04 to detect a difference. If 15 patients or more obtain a major response, then the study would be a success, if 14 patients or fewer obtain a major response, then the study would be a failure and the combination should not continue further evaluation. Sample size and power estimation were obtained using the binomial method (STATA version 13).

Accrual time will be approximately 12-18 months, at a rate of 2-3 patients per month. Patients will be followed for the duration of time on active protocol therapy (47 cycles), and then 2 additional years after completion of cycle 47. Participants will be followed for up to 24 months after completion of protocol therapy, or until termination from study, disease progression, initiation of new anti-neoplastic therapy, or death. Participants removed from protocol therapy for unacceptable adverse event(s) will be followed until resolution of the adverse event to at least grade 1 or less, or stabilization of the adverse event.

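### Section 6 makes plasmapheresed patients inevaluable for response with no stated end; with the replacement rule, this takes them out of the evaluable denominator, in conflict with 11.1.1 and 13.5

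*Combined protocol and SAP*

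**What the plan says.** **Section 6, Potential for IgM flare.** IgM is said to return to steady state 4-5 weeks after plasmapheresis. The next sentence reads: "As such WM patients will be invaluable for response purposes". Plasmapheresis is described for symptomatic flares. Before treatment, the text says: "It is recommended patients with symptomatic hyperviscosity or a pre-treatment serum IgM level >4,000 mg/dL undergo plasmapheresis before treatment with ulocuplumab".

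**Section 13.2.** The design is stated as "a sample of 20 patients would have a power of 80% with an alpha of 0.04", for a major response rate of 50% against 80%. The rule is "If 15 patients or more obtain a major response, then the study would be a success", on 20 evaluable patients. On evaluability and replacement it says "To be evaluable for response, patients must have one cycle of therapy" and "Patients inevaluable for response will be replaced".

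**Section 13.7.2.** It repeats the replacement rule and rests all conclusions on evaluable participants.

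**Section 11.1.1.** Those evaluable for response are "Only those participants who have measurable disease present at baseline, have received at least one cycle of therapy, and have had their disease re-evaluated". Plasmapheresis is not mentioned.

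**Section 13.5.** The primary major response proportion is calculated in the full analysis set (FAS), which holds everyone who received at least one dose.

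**The concern.** The same plasmapheresed participant is inevaluable under Section 6, evaluable under 11.1.1 if the cycle and re-evaluation conditions are met, and in the FAS under 13.5. If Section 6 is followed as printed, 13.2 then replaces that participant.

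Two groups are affected. One is defined before treatment: symptomatic hyperviscosity or IgM above 4,000 mg/dL. It includes patients whom 3.1.1 admits as high risk on an IgM of 6,000 or more, since they all exceed the plasmapheresis threshold. The other is defined after treatment starts: participants plasmapheresed for a symptomatic flare. Replacing the second group conditions the response rate on a post-baseline event that may be an early effect of the study drug. The success rule would then be applied to a selected set of patients.

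**Working it through.** **1. The plan's own figures.** Inputs from 13.2: n = 20, success at 15 or more, rates 50% and 80%. With X binomial:

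- P(X ≥ 15 | 20, 0.5) = (15504 + 4845 + 1140 + 190 + 20 + 1) / 2^20 = 21700 / 1048576 = 0.0207 one-sided. Doubled, this is 0.0414, which rounds to the stated 0.04.
- P(X ≥ 15 | 20, 0.8) = 0.804, against the stated 80%.

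The design reproduces.

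**2. How many could be affected.** The documents give no plasmapheresis rate for this trial. Section 2.3 gives two indications from the earlier single-agent ibrutinib study.

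- Five of 63 (four with hyperviscosity, one with factor VIII deficiency) needed plasmapheresis: 8%, or 1.6 per 20.
- Median IgM was 3,520 mg/dL, and 46 of 63 (73%) were at 3,000 or more. Assuming a lognormal distribution, sigma = ln(3520/3000) / 0.613 = 0.261, and P(IgM > 4,000) = 1 − Φ(ln(4000/3520) / 0.261) = 0.31, or about 6 per 20.

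The range is therefore roughly 2 to 6 of 20. The upper end assumes that everyone above 4,000 mg/dL follows what is only a recommendation.

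**3. Effect on the 15-of-20 rule if they are replaced.** Let p be the true major response rate in all treated patients, q the share removed, and r the rate among those removed. The rate among those kept is (p − q·r) / (1 − q). The documents give neither q nor r, so both are assumed. With p = 0.50:

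| q | r | rate among those kept | P(X ≥ 15 of 20), one-sided |
|---|---|---|---|
| any | 50% | 0.500 | 0.021 |
| 10% | 30% | (0.50 − 0.03)/0.90 = 0.522 | 0.033 |
| 20% | 30% | (0.50 − 0.06)/0.80 = 0.550 | 0.055 |
| 30% | 30% | (0.50 − 0.09)/0.70 = 0.586 | 0.101 |
| 10% | 0% | 0.50/0.90 = 0.556 | 0.061 |

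The last row is an extreme case.

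**4. How far the two denominators diverge.** To reach 20 evaluable patients, 20q/(1 − q) others are treated and replaced: 2.2, 5.0 or 8.6 at q = 10%, 20% or 30%. Suppose 15 of the 20 evaluable respond, and suppose the FAS counts those replaced as non-responders (an assumption; 13.5 does not say).

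| Denominator | Rate | Exact 95% CI |
|---|---|---|
| 15/20 (evaluable) | 75% | 51%–91% |
| 15/22 | 68% | 45%–86% |
| 15/25 | 60% | 39%–79% |
| 15/29 | 52% | 33%–71% |

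The same data can meet the success rule in 13.2 while the 13.5 interval includes 50%.

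**The case against.** The strongest reply is that Section 6 was never meant to remove anyone. The sentence follows directly from the 4-5 week recovery time, so a temporary reading is natural. Section 11.1.2 treats drug holds that way: the IgM values, not the patient, become unevaluable. With 47 four-week cycles planned, a gap of 4-5 weeks would not by itself stop a later major response from being counted. This is probably the intent and it stands as such, but the sentence names patients and gives no period, and nothing in Sections 11 or 13 supplies one.

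Three stronger readings are tempting and are not supported.

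- *That these patients leave the primary analysis.* Section 13.5 places the primary proportion in the FAS, which keeps them. The documents conflict; they do not settle on exclusion. The exclusion bears on the evaluable denominator of 13.2 and 13.7.2.
- *That the response rate is biased upward.* For high baseline IgM, Section 2.3 reports similar overall responses below 4,000 mg/dL and at or above it, and similar major responses across most baseline subgroups. All five plasmapheresed patients in that study responded, although it does not say that these were major responses. Section 2.3 therefore gives no sign of poorer response in the group that could make up the larger shares in the table. Upward bias is plausible only for removal after an on-treatment flare.
- *That everyone who flares is removed.* Only flares treated by plasmapheresis are affected. The flare evidence cited in Section 6 concerns anti-CD20 antibodies and intravenous immunoglobulin, and no ulocuplumab flare rate is given.

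**Conclusion.** The concern holds as a conflict in the written plan. Section 6 has a patient-level exclusion without an end, 13.2 and 13.7.2 turn inevaluability into replacement, and 11.1.1 and 13.5 keep the same patients. Taken literally, the exclusion includes removal after a post-baseline event, so the major response rate may be too high; the documents do not show that it would be.

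The size runs from no distortion (0.021) to 0.101 over assumed shares of 10% to 30% with a 30% response among those removed. The 0.061 rests on 10% removed and no responder among them. None of these shares or response rates comes from the documents, and the direction is open for the high-baseline-IgM group.

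Sections 1.1 and 5.1 record that Phase II never opened, so no Phase II result was affected.

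**What to change.** Replace the Section 6 sentence by: *IgM values within 5 weeks after a plasmapheresis are not used for response classification; the participant remains evaluable and is not replaced.* This uses the upper end of the protocol's own 4-5 week figure and changes no treatment.

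Three additions are needed for it to work:

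- State that the baseline IgM for response is the last value before any pre-treatment plasmapheresis. Section 6 allows ulocuplumab to be delayed by up to two weeks for plasmapheresis, so a Day 1 value can fall inside the excluded window.
- Refer to the rule from 11.1.1, 13.2, 13.5 and 13.7.2, and make these sections use the same denominator.
- With any reported response rate, give the number of participants plasmapheresed and their responses.

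The cost is one replaced sentence, one baseline definition, four cross-references and one reporting line. The downside is that response may be dated later in these participants.
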